3.5. RANDOMIZATION AND BLINDING

Central randomization will be implemented in this study using an IWRS. Randomization will be stratified based on transfusion burden (4 or >4 units) prior to randomization, and then assigned randomly on a 1:1 basis to receive either talacotuzumab or daratumumab. Transfusion burden is defined as the maximum number of RBC units transfused over any 8 consecutive weeks during the 16 weeks prior to randomization. However, due to safety concerns, enrollment to the talacotuzumab arm was closed (refer to Section 3.1 Overview of Study Design for details).

3.6. CHANGE IN STUDY CONDUCT

Enrollment to the talacotuzumab arm was closed based upon the occurrence of a Grade 4 infusion-related reaction in the first subject who received talacotuzumab. All analyses and summaries described in this document will include data only in subjects who received daratumumab. Data listings will be provided separately for the single subject who received talacotuzumab.

4. GENERAL DESCRIPTIONS AND DEFINITIONS

4.1. BASELINE AND STUDY PHASES

Baseline Value: Unless specified otherwise, the baseline value is defined as the last non-missing value collected on or before the first dose.

Screening Phase: Up to 28 days prior to the first dose of study drug, during which subject eligibility will be reviewed and approved by the sponsor.

Treatment Phase: Between the date of first dose until study drug discontinuation. The Treatment Phase will be divided by cycles, based on the nominal treatment cycles as recorded on the CRF. Each cycle is planned to be 28 days.

Post-treatment Follow-up Phase: After the End of Treatment Phase until the end of study participation or end of study, which is defined as 1 year after randomization of the last subject or anytime the Sponsor terminates the study, whichever comes first.

4.2. STUDY DAY AND CONVENTION OF TIME COMPUTATIONS

Study Day 1 is defined as the day of first dose.

Study Day = assessment date – Study Day 1 + 1 for assessments performed on or after Study Day 1; Study Day = assessment date – Study Day 1 for assessments performed before Study Day 1.

Cycle Day = assessment date – date of the first dose for the cycle + 1.

By convention, one month equals to 30.4375 days and one year equals to 365.25 days. Duration in days between 2 timepoints will be calculated as (end date – start date + 1).

4.3. ANALYSIS SETS

Intent-to-Treat (ITT) analysis set: includes all subjects who are assigned to receive daratumumab. This analysis set will be used for all summaries of disposition, demographic, baseline disease characteristics, and efficacy analyses.

Safety analysis set: includes all subjects who receive at least one dose of daratumumab. This analysis set will be used for all safety analyses and analyses of exposure.

5. SUBJECT INFORMATION

5.1. DEMOGRAPHICS AND BASELINE CHARACTERISTICS

All demographic and baseline characteristic variables will be summarized for the ITT analysis set.

The stratification factors used during randomization (prior RBC transfusion burden) will be tabulated.

Two panels of baseline clinical laboratory tests specified will be summarized: hematology and serum chemistry. Frequencies of National Cancer Institute (NCI) Common Terminology Criteria for Adverse Events (CTCAE) grade at baseline will be reported.

Disease characteristics to be summarized will include WHO classification, IPSS risk category (low, intermediate-1), prior ESA treatment (Yes, No), serum EPO level (≤ 500 mU/mL, > 500 mU/ml), and time since initial diagnosis (months).

Hepatitis serology tests at baseline will be summarized by test type and results.

Transfusion history summaries will include total transfusion units, and prior RBC transfusion burden (4, >4 units). Prior RBC transfusion burden is defined as the maximum number of RBC units transfused over an 8-week period during the 16 weeks prior to Study Entry.

Medical history will be summarized including abnormality in physical examination.

In addition, summaries of bone marrow findings at baseline will be provided.

5.2. DISPOSITION INFORMATION

Subject enrollment will be summarized by country and investigator.

Disposition information will be summarized for the ITT analysis set at the end of treatment and at the end of study, respectively.

5.3. EXTENT OF EXPOSURE

All exposure summaries are to be presented for the Safety analysis set.

The number of treatment cycles received will be summarized along with the duration of treatment exposure; dose intensity, which is equal to the sum of the total dose (mg/kg) received in all cycles divided by the number of cycles received; relative dose intensity, which is defined as intensity of total actual dose / intensity of total planned dose; and incidence of dose modifications (aborted infusion, infusion interruption, reduced dose, infusion delay within the cycle, and cycle delay), as well as reasons of dose modifications. Skipped doses are not captured in the database but will be derived and reviewed by study team physicians and provided in a data listing.

5.4. PROTOCOL DEVIATIONS

Subjects with major protocol deviations will be listed. Protocol deviations will be based on clinical review mainly on the following aspects (but not limited to): (1) eligibility criteria, (2) treatment compliance, and (3) prohibited concomitant medication. Protocol deviations will be closely

monitored during the execution of the study and the final set of protocol deviation criteria will be finalized before database lock.

5.5. PRIOR AND CONCOMITANT MEDICATIONS

Medications administered prior to the first dose of study drug will be considered prior medications. Concomitant therapies include those taken on or after first dose date through 30 days after last dose of study drug. Using this definition, a medication can be classified as both prior and concomitant.

Use of prior and concomitant medications will be summarized by Anatomical Therapeutic Chemical (ATC) class and drug generic term. Prior anticancer therapy will be summarized by type (e.g., radiotherapy, surgery, chemotherapy). Best response to prior ESA therapy will also be summarized.

Concomitant therapies of special interest will be summarized, including: myeloid growth factors [e.g., granulocyte-colony stimulating factor (G-CSF)], anticoagulants and antiplatelet agents. Other concomitant therapies, including anti-infectives (antibacterials, antivirals, and antimycotics), corticosteroids, anti-arrhythmics and other cardiac supportive therapy, anti-histamines, anti-emetics, anti-diarrheals will be summarized.

6. EFFICACY

6.1. PRIMARY EFFICACY ENDPOINT

6.1.1. DEFINITION

The primary efficacy endpoint is the rate of RBC TI lasting for at least 8 weeks. The 8-week RBC TI rate is defined as the proportion of subjects without any RBC transfusion during any consecutive 8 weeks (56 days) starting from Study Day 1 until the end of study. The starting date of 8-week RBC TI must be between Study Day 1 and End of treatment Phase ending date (date of last dose of study medication + 30 days).

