Transfusion history and status; myeloid growth factor treatment	Assessment of RBC transfusion requirements and myeloid growth factor use 16 weeks prior to randomization, at each 4-week cycle visit, disease evaluation visit, and all unscheduled visits during treatment. Complete transfusion information must be collected, including both in-patient and out-patient transfusions	X	X ^a		Only Day 1 ^a	Only Day 1 ^a	Only Day 1 ^a	X	X (first visit and every 4-6 weeks if feasible)

TIME AND EVENTS SCHEDULE - DARATUMUMAB

PHASE	Study Procedures	Notes	Screening Phase	Treatment Phase (4-week cycles +/-3 days)					Posttreatment Follow-up Phase	
			Up to 28 days before first dose	Cycle 1 Day 1	Cycle 1 Day 8, 15, 22	Cycle 2 Day 1, 8, 15, 22	Cycle 3, 4, 5, 6 Day 1, 15	Cycle 7 until EOT Day 1	EOT Visit Within 30 days after last dose	Survival Follow-up Every 16 weeks (+/- 7 days)
	Bone marrow aspirate with cytogenetics and bone marrow biopsy	Bone marrow aspirate and biopsy with iron stain must be performed during screening or up to 12 weeks prior to first dose. Following the bone marrow at PR and CR, bone marrow should be repeated 4 to 8 weeks later for confirmatory purposes. The EOT bone marrow does not have to be performed if the prior assessment occurred within 8 weeks. Bone marrow assessments can be performed within a window of ± 7 days.	X	Every 24 weeks, at time of PR, CR, and at PD If PR/CR occurs, a bone marrow is collected every 24 weeks thereafter					X	
	Response assessment	Per IWG 2006		Week 12, 24, 36, 48, 60, 72 and then every 24 weeks until PD					X	
	ECOG performance status		X	X ^a		Only Day 1 ^a	Only Day 1 ^a	X ^a	X	
	Survival status									X
	Biomarker Assessments									
	Bone marrow biopsy	See Efficacy Assessments Section	X							
	Bone marrow aspirate	See Efficacy Assessments Section	X	At time of suspected PR/CR and every 24 weeks thereafter until PD					X (or PD)	
	Peripheral blood	Peripheral blood will be collected at specified visits and at the time of PR/CR and every 24 weeks thereafter. Immunophenotyping will be performed by flow cytometry and CyTOF.		X ^a	Only Day 15 ^a	Only Day 1 ^a	Only Day 1 of Cycles 4 and 6 ^a		X (or PD)	
	Plasma	Plasma will also be collected at specified visits and at the time of PR/CR and every 24 weeks thereafter.		X ^a			Only Day 1 of Cycle 4 ^a		X (or PD)	

TIME AND EVENTS SCHEDULE - DARATUMUMAB

PHASE	Notes	Screening Phase	Treatment Phase (4-week cycles +/-3 days)						Posttreatment Follow-up Phase

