			Cycle 1 Day 1	Cycle 1 Day 8, 15, 22	Cycle 2 Day 1, 8, 15, 22	Cycle 3, 4, 5, 6 Day 1, 15	Cycle 7 until EOT Day 1	EOT Visit Within 30 days after last dose	
Study Procedures		Up to 28 days before first dose							Survival Follow-up Every 16 weeks (+/- 7 days)
Clinical Laboratory Assessments									
Hematology	Hematology laboratory assessments to determine subject eligibility must be performed within 14 days prior to first dose. For Cycle 1 Day 1, clinical laboratory assessments do not need to be repeated if the Screening tests were performed within 5 days of the first dose of study treatment.	X	X ^a	X	Only Day 1 ^a	Only Day 1 ^a	X	X	
Chemistry	Chemistry laboratory assessments to determine subject eligibility must be performed within 14 days prior to first dose. For Cycle 1 Day 1, clinical laboratory assessments do not need to be repeated if the Screening tests were performed within 5 days of the first dose of study treatment.	X	X ^a		Only Day 1 ^a	Only Day 1 ^a	X ^a	X	
Blood type assessment and indirect antiglobulin results	Prior to dosing on Day 1 of Cycle 1 only								
Serum EPO level		X							
Serum ferritin, transferrin saturation		X							
Serology	HIV antibody, hepatitis B surface antigen, and hepatitis C virus antibody	X							
Serum β -hCG or urine pregnancy test	For women of childbearing potential only; must be performed within 14 days prior to first dose	X	Only if clinically indicated						
Ongoing Subject Review									
Concomitant therapy	Continuous from the time of signing ICF until 30 days after the end of dosing or until the start of subsequent anticancer treatment, if earlier	X			Continuous			X	

TIME AND EVENTS SCHEDULE - DARATUMUMAB

PHASE	Notes	Screening Phase	Treatment Phase (4-week cycles +/-3 days)					Posttreatment Follow-up Phase	
		Up to 28 days before first dose	Cycle 1 Day 1	Cycle 1 Day 8, 15, 22	Cycle 2 Day 1, 8, 15, 22	Cycle 3, 4, 5, 6 Day 1, 15	Cycle 7 until EOT Day 1	EOT Visit Within 30 days after last dose	Survival Follow-up Every 16 weeks (+/- 7 days)
Adverse events	Continuous from the time of signing ICF until 30 days after the end of dosing or until the start of subsequent anticancer treatment, if earlier	X	Continuous					X	
Subsequent therapy	Subsequent therapy to be collected throughout survival follow-up period							X	X
Abbreviations: C1D1=Cycle 1, Day 1; CR=complete remission; CyTOF=cytometry by time of flight; EOT=end-of-treatment; EPO=erythropoietin; PD=disease progression; PR=partial remission									

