8.2. Concomitant Medications

Subjects should receive supportive care as clinically indicated. This includes blood product support (blood transfusions and use of granulocyte colony stimulating growth factors), anti-diarrheals, anti-emetics, analgesics, anti-infective treatment, and treatment of other medical conditions.

The following medications are prohibited during the study: ESA therapy, chemotherapy (anticancer), immunomodulatory drugs, immunotherapy, experimental therapy, and radiotherapy. Systemic use of corticosteroids in excess of prednisone 20 mg/day or its equivalent for more than

10 days is prohibited unless reviewed and approved by the sponsor. Long-term, chronic use of corticosteroids at any dose should also be reviewed and approved by the sponsor. Corticosteroids used as premedication are permitted. The sponsor must be notified in advance (or as soon as possible thereafter) of any instances in which prohibited therapies are administered.

All concomitant therapies (prescription or over-the-counter medications, including vaccines, vitamins, herbal supplements), including growth factors, transfusions, anti-infectives (antibacterials, antivirals, and antimycotics), corticosteroids, anti-arrhythmics and other cardiac supportive therapy, anti-histamines, anti-emetics, anti-diarrheals, and anti-coagulants must be recorded throughout the study beginning with signing of the ICF to 30 days after the end of dosing or until the start of subsequent anticancer treatment, if earlier. Modification of an effective preexisting therapy should not be made for the explicit purpose of entering a subject into the study. Concomitant therapies should be recorded beyond 30 days after the last dose of study treatment only in conjunction with new or worsening adverse events or serious adverse events that meet the criteria outlined in Section 12.3.2, Serious Adverse Events. The follow-up of subjects in the study and study data collection will end either 1 year after the last subject is randomized or anytime the sponsor terminates the study. Subjects who are continuing to derive benefit from daratumumab treatment as assessed by their investigator may continue to receive daratumumab according to the protocol. During this period after study data collection has ended, only serious adverse events will be monitored and only entered into the company safety repository as described under Amendment 4 and in the Time and Events Schedule.

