9.2.1. Transfusions

Data to be collected at each visit include the number of units and type of blood products transfused and the pre-transfusion hemoglobin and platelet count. Transfusion data will be collected during the treatment and posttreatment periods as specified in the Time and Event Schedules. Transfusion is monitored at each visit for infusion (every 4-week cycle), at each disease evaluation visit, and at all unscheduled visits during treatment. During the posttreatment phase, transfusion data will be collected every 4 to 6 weeks. Specific operational monitoring will be implemented to seek transfusion information from other documented sources. Specific and continuous medical review will be implemented to identify any sudden but unsustained increase

of Hb values and to query whether transfusion has occurred. Red blood cell transfusions may be administered based on hemoglobin level (sponsor should be notified for Hb >11 g/dL), investigator's assessment of the subject's clinical signs and symptoms, and local clinical practice.

As the volume of 1 unit of RBC transfusion may vary regionally, 1 unit is defined as the amount that is intended to raise Hb by approximately 1 g/dL in an adult patient (ie, 1 standard pRBC unit or equivalent). The total number of RBC units required over consecutive 8-week time periods will be calculated to identify subjects who achieve RBC TI or transfusion reduction.

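### The TI definition has no stop at subsequent MDS therapy, and the protocol is unclear on whether transfusions are still recorded then, so a transfusion-free period under a later drug can count as a daratumumab response

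*SAP*

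**What the plan says.** **Window.** SAP 6.1.1 counts a subject as a responder if he or she is "without any RBC transfusion during any consecutive 8 weeks (56 days) starting from Study Day 1 until the end of study". Its one limit is on the beginning of the window: "The starting date of 8-week RBC TI must be between Study Day 1 and End of treatment Phase ending date", defined as last dose plus 30 days. SAP 6.2.1 uses the same start limit for 24-week TI and for the 8-week intervals behind best transfusion reduction. It censors duration of TI at the last transfusion evaluation. None of these rules mentions subsequent therapy, and neither does the endpoint definition in Protocol 2.1.2.

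**Subsequent therapy.** Protocol 9.1.3 asks that the End-of-Treatment Visit, due within 30 days of the last dose, be completed before any new MDS treatment. The Time and Events Schedule collects subsequent therapy through survival follow-up.

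**Recording of transfusions.** Protocol 8.2 lists, among the therapies to be recorded, items "including growth factors, transfusions, anti-infectives" and others, from consent "to 30 days after the end of dosing or until the start of subsequent anticancer treatment, if earlier". It adds: "Concomitant therapies should be recorded beyond 30 days after the last dose of study treatment only in conjunction with new or worsening adverse events". The same exception covers events that are serious. The daratumumab schedule has the same stop for concomitant therapy: "until 30 days after the end of dosing or until the start of subsequent anticancer treatment, if earlier". Against this, Protocol 9.2.1 says: "During the posttreatment phase, transfusion data will be collected every 4 to 6 weeks". The schedule's transfusion row says "first visit and every 4-6 weeks if feasible".

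**Missing assessments.** Under SAP 6.1.2 a window with any missing transfusion assessment does not qualify.

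**The concern.** A subject who stops daratumumab, starts another drug within 30 days and then becomes transfusion-free can satisfy the definition as written. SAP 3.6 restricts the analysis to daratumumab, so no concurrent arm carries the same error. The omission looks unintended, because SAP 7.1 does cut the treatment-emergent adverse event window at subsequent anti-cancer therapy.

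The decision rule is sensitive to single subjects: 5 against 6 responders separates not met from inconclusive, and 7 against 8 separates inconclusive from met. For an inconclusive result SAP 3.4 turns to sensitivity analyses and other endpoints. The one sensitivity analysis described (Protocol 11.3) admits shorter transfusion-free periods. It can only add responders, so it cannot reveal this bias.

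The recording conflict matters because it decides, through SAP 6.1.2, whether such a window is complete.

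**Working it through.** **1. The plan's own rule.** With a Beta(0.5, 0.5) prior and N = 30, the posterior is Beta(0.5+m, 30.5−m). All 11 rows of SAP Table 1 reproduce. The rows at the boundaries are:

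| m | 80% credible interval (%) | P(rate ≤ 15%) | Category |
|---|---|---|---|
| 5 | 9.6 to 26.8 | 0.378 | not met |
| 6 | 12.2 to 30.6 | 0.214 | inconclusive |
| 7 | 14.8 to 34.3 | 0.105 | inconclusive |
| 8 | 17.6 to 37.9 | 0.045 | met |

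At a true rate of 15%, the binomial P(m ≥ 8) is 0.0698. The count falls on 5 or 7 with probability 0.186 + 0.083 = 0.269.

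**2. Window dates (last dose = day 0).** The latest permitted start is day +30, and 56 days inclusive end on day 30 + 55 = +85. If Protocol 8.2 governs and recording ends by day +30, a complete window must start by day 30 − 55 = −25, so the SAP's 30-day allowance could never be used. If Protocol 9.2.1 governs, windows up to day +85 can be complete, including after a switch.

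**3. How narrow the route is.** Suppose the stop is decided at the next scheduled dose. The days left before day +30 are then 30 − 7 = 23 (weekly dosing), 30 − 14 = 16 (2-weekly) or 30 − 28 = 2 (4-weekly).

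The cutoff is 6 × 30.4375 ≈ 183 days after the last randomization. Taking study day as days from randomization:

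- Stop at Cycle 7 Day 1 (day 169; last dose Cycle 6 Day 15 = day 155): windows start on days 170 to 185 and end on days 225 to 240. The subject must have been randomized at least 225 − 183 = 42 to 240 − 183 = 57 days before the last subject.
- Stop at Cycle 8 Day 1 (day 197; last dose day 169): windows start on days 198 to 199 and end on days 253 to 254, a lead of 70 to 71 days.

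Stops for progression, safety or refusal (Protocol 10.2) can come earlier.

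**4. Size.** Let q = p + (1−p) × s × r × o × e, where:

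- p is the true daratumumab TI rate;
- s is the share of non-responders who switch within 30 days: 20% to 40%, assumed;
- r is the later drug's TI rate: 17% (azacitidine) to 27% (lenalidomide), both from Protocol Section 1;
- o is the share of those TI periods starting by day +30: 10% to 25%, assumed;
- e is the share of switchers whose window is complete and ends by the cutoff: 1, 0.5 or 0.25, assumed.

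The low corner is 0.20 × 0.17 × 0.10 = 0.0034 and the high corner 0.40 × 0.27 × 0.25 = 0.027. At e = 1 and p = 0.15, q = 0.15 + 0.85 × 0.0034 = 0.153 to 0.15 + 0.85 × 0.027 = 0.173. Added responders are 30 × 0.85 × 0.0034 = 0.09 to 30 × 0.85 × 0.027 = 0.69. Results at p = 0.15:

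| e | P(m ≥ 8) | Added responders per 30 | Moves up at least one category | Moves into met |
|---|---|---|---|---|
| 1 (upper bound) | 7.7–13.4% | 0.09–0.69 | 2.3–18.8% | 0.7–6.4% |
| 0.5 | 7.3–9.9% | 0.04–0.34 | 1.1–9.2% | 0.3–2.9% |
| 0.25 | 7.1–8.3% | 0.02–0.17 | 0.6–4.5% | 0.2–1.4% |

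A jump from not met to met occurs in at most 0.65% of trials. At p = 7.5%, the SAP's best-supportive-care rate, P(m ≥ 8) goes from 0.13% to at most 0.78%. At 2.5%, the protocol's figure, it stays at or below 0.01%.

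**The case against.** The SAP already tightens the protocol's definition: a window must begin by day +30 and have no missing assessment. To be misattributed, a subject must stop, have the End-of-Treatment Visit, start a new drug and begin a transfusion-free run, all within days to about three weeks. These are subjects who entered needing at least 4 units in 8 weeks. Protocol Section 6 places the discussion of continuing without benefit at 6 months, when dosing turns 4-weekly and only about 2 days remain. The protocol says there is no universally accepted option for most of these patients, which points to low switching. The size rests largely on assumed inputs, and the 27% chance of sitting on 5 or 7 matters only if an extra responder actually occurs. All of this stands, and it is why the effect is described as probably small.

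It is also argued that the recording conflict answers itself: Protocol 9.2.1 is the specific rule and should prevail, and if 8.2 prevails instead, post-switch windows are incomplete and drop out. But the first reading leaves the gap open, while the second closes it for windows running past a switch only by making the SAP's 30-day allowance empty. The documents do not say which applies. Listing deviations under SAP 5.4 does not remove a subject from the TI count. The 6-month cutoff narrows the route without closing it, and SAP 6.1.1 itself runs to the end of study, one year after the last randomization.

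Finally, a full stop at new therapy makes a non-responder of a subject who switches partway through a genuine daratumumab window. That cost is real, and it is the reason to report the count both ways.

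**Conclusion.** The concern holds and should be fixed. As written, the rule can credit a later drug's effect to daratumumab, and the same gap affects 24-week TI, duration of TI and best transfusion reduction. The direction is upward. At a true 15% rate, the chance of a met result rises from 7.0% to 7.1–8.3% if a quarter of switchers can contribute, 7.3–9.9% if half can, and 7.7–13.4% as an upper bound. The switching, onset and completeness shares are assumptions, and the low end is the more plausible for switching.

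An inactive drug is not pushed to met. These are frequentist probabilities; they show no breach of the SAP's 10% criterion, which is a posterior probability (4.5% at 8 responders). Confidence is medium: the gap in the text is clear, but how often it would be used is not known.

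**What to change.** 1. In SAP 6.1.1 and 6.2.1, require all 56 (or 168) days to be completed before the first dose of any subsequent MDS therapy. Apply the same stop to the 8-week intervals for best transfusion reduction, and censor duration of TI at that date.
2. Report the TI count with and without the stop.
3. Reconcile Protocol 8.2 and the schedule's concomitant-therapy row with Protocol 9.2.1 and the schedule's transfusion row. State how long transfusions are recorded after the last dose and after new therapy begins, and what counts as a missing assessment when post-treatment collection depends on feasibility.
4. State in SAP 6.1.1 that the primary decision uses data up to the 6-month clinical cutoff (Protocol 9.1.5, SAP 3.1), not to the end of study.

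The cost is SAP wording, one date already collected, one table row and one clarifying sentence. N = 30 and the threshold of 8 do not change. The TI rate may fall slightly, and a subject who switches partway through a genuine daratumumab window loses responder status; the two counts side by side make that visible.
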